In the proposed study, a sample of young adult (21-24 years) exclusive EC users with no or minimal history of smoking (n=75) and older adult (25-50 years) smokers (n=75) will complete a single-visit, double-blinded, within-subject randomized crossover trial. Participants will vape e-liquids containing varying freebase (FB) nicotine fractions (5, 25, 45, 65, 85%) at 20 or 50 mg/mL concentrations. The FB fractions were selected to cover a wide range with the lower end consistent with JUUL and disposable pod-based ECs that are popular among youth¹¹ and the higher end resembling early ECs that were FB nicotine-based and less appealing to young people. Each of the 10 conditions will be tested in a 2-puff session, followed by rating the appeal and sensory attributes, with a 10-minute washout period between conditions. Previous studies used a similar study design to examine the appeal of EC flavors, nicotine concentrations, and interactive effects of flavor and nicotine.¹²⁻¹⁵ For example, in a study of young adult current EC users,¹² the sensory appeal of ECs decreased as nicotine concentration increased but was not affected by flavoring. Another study of current EC users or smokers reported higher ratings of appeal for salt nicotine vs. free-base nicotine across different flavors, and salt nicotine decreased perceived harshness more among never smokers than ever smokers.¹⁵ While these studies shed light on the effect of nicotine salts and concentration on the sensory experience of EC use, their design was limited in ability to evaluate the effect of granular fractions of nicotine salts. This study will fill the gap in the literature by examining the effect of five free-base levels of nicotine at two nicotine concentration levels and determining the 'sweet spot' level of free-base nicotine that can be tolerated by smokers but not by non-smokers.

B. Study Procedures

Participants will be screened initially through an online screener, which will be linked to our study advertisement and administered using REDCap. Eligible participants interested in participating will be scheduled for the study visit via phone or e-mail. Participants will be instructed that they must remain nicotine abstinent for 12 hours before their visit and will receive a reminder the evening before.

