Vaping sessions will take place after collecting biospecimens and completing questionnaires on sociodemographics, tobacco use history, and dependence on ECs and cigarettes. Guided by study staff, participants will take two puffs of each of the 10 study conditions (5 freebase nicotine fractions \times 2 nicotine concentrations) using the study EC device, followed by a 10-minute washout period between conditions. During the washout period, participants will be instructed to rinse their mouths and spit three times with room-temperature water before sampling the next preparation to minimize carryover effects. The washout period was deemed sufficient based on an arterial study showing a return to baseline plasma nicotine levels 40 minutes following a 10-puff vaping session (hence, 4 minutes are needed for nicotine levels to return to baseline after each puff).²² Participants will be provided pre-filled and weighed e-liquid pods in random order. Participants will be instructed to inhale for at least 1 second for each puff, but other puffing parameters (i.e., flow rate, maximum puff duration, puff volume, rate of exhalation) will not be controlled.

After each condition, participants will complete General Labeled Magnitude Scale (gLMS)¹⁴ and Labeled Hedonic Scale²³ to rate the degree of liking or disliking of sensations and the strength of sensory attributes of e-liquids including throat hit, smoothness, harshness, sweetness, and bitterness. Participants will also rate overall acceptance on a tobacco industry-designed thermometer scale (from 0 "the very worst" to 100 "the very best", with 50 indicating "indifferent").²⁴ Drug Effects/Liking Questionnaire,²⁵ the modified Cigarette Evaluation Questionnaire (mCEQ), and the adapted version of behavioral intentions for continued use (from 1 "extremely unlikely" to 7 "extremely likely")²⁶ will also be collected to assess subjective responses to ECs (e.g., reward, satisfaction).²⁷

All study visits will take place at the OSUCCC's Center for Tobacco Research, where participants will complete a consent form, screening procedures, vaping sessions, and online questionnaires and surveys on a tablet.

C. Recruitment

1) Number of Participants

A total of 150 participants will be recruited, including young adult e-cigarette (EC) users with minimal or no history of smoking (n=75) and older adult smokers (n=75).

2) Participant Population

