The primary goal of the study is to identify a nicotine fraction limit that is appealing to smokers with a minimal appeal to young adult EC users. Generalized linear mixed models will be employed for measures of appeal (e.g., industry thermometer rating and sensory appeal metrics). Models will include demographic and smoking history as covariates, random effects for subject, main effects for user group (smokers vs. EC use), FB fraction (numeric), and concentration (categorical), and interaction effects between smoking group and each of the condition parameter variables (i.e., FB fraction and concentration). A significant interaction between smoking group and a condition parameter variable would indicate that the variable differentially affects appeal between the two user groups. Because of multiple measurements tested, we will assume a significance threshold of $p=0.01$. Conservatively, considering 120 participants, a correlation of 0.5, and $\alpha=0.01$, a two-sided paired t-test achieves 80% power to detect an effect size of 0.32 standard deviations of the measurement for the concentration main effect. For FB fraction, with 120 subjects, the model achieves 80% power to detect a slope of 0.31, considering $\alpha=0.01$. We estimate the power for the categorical interactions by pairwise comparisons of the two interacting groups (with two 2-level variables there are a total of 4 groups) and adjust the p-value to account for the 6 possible pairwise comparisons ($0.01/6=0.0017=p$). With 30 samples per group, a two-sided, two-sample t-test achieves over 80% power to detect a 1.7-fold difference between any of the two groups in the interaction term, considering $\alpha=0.0017$ and coefficient of variation=0.5. For interactions with FB fraction, group sizes of 60 achieve 80% power to detect a difference in slopes of 0.43, considering $\alpha=0.01$. Interactions between condition parameter variables will also be explored. Since our goal is to find combinations of the condition parameter that are appealing to smokers but not young adult EC users, we will compare condition combinations directly to identify the condition parameter combinations that result in the largest difference in appeal between

the two user groups. Carryover effects will be explored by estimating the interaction of a given condition with the preceding treatment and period effects tested by the interaction of treatment with order.

III. Data and Safety Monitoring Plan

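### The order of the ten conditions is left at random order, with no required balance for session position or preceding condition, although the planned analyses depend on both; a blocked Williams scheme with fresh labels per block gives that balance at almost no cost.

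*Combined protocol and SAP*

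**What the plan says.** Section II.A describes participants who "will complete a single-visit, double-blinded, within-subject randomized crossover trial". Under Section II.B, "participants will take two puffs of each of the 10 study conditions", with 10 minutes between conditions and after 12 hours without nicotine. On sequence, the only instruction is: "Participants will be provided pre-filled and weighed e-liquid pods in random order". Neither section mentions a sequence set, blocking, stratification by user group, or balance for position or predecessor.

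Section II.C sets 75 participants per user group. Section II.B provides that participants who later fail the NNAL or plasma nicotine criterion are replaced, without saying which order the replacement receives.

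Three analyses in Section II.E depend on sequence:

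- "Carryover effects will be explored by estimating the interaction of a given condition with the preceding treatment".
- Period effects are to be tested through a treatment-by-order interaction.
- Condition combinations are to be compared directly, to find those whose appeal separates the two groups most.

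The listed mixed model contains covariates, a subject effect, group, free-base fraction, concentration and the group interactions. Period is not among its terms.

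**The concern.** In a ten-period, single-visit crossover, the order of administration is the main design tool against drift and carryover. Both are plausible here. Participants arrive abstinent and take nicotine ten times. By the protocol's own reckoning of 4 minutes per puff, two puffs use 8 of the 10 washout minutes, and that reasoning covers plasma nicotine rather than lingering sensation.

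As written, the plan permits an independent permutation for each participant. Some ordered pairs of conditions would then hardly be seen within a group, which weakens the predecessor analysis wherever a thin cell falls. Conditions would also differ by chance in how early or late they were rated, and the listed model does not adjust for that. Choosing the combination with the largest between-group difference tends to favour whichever combination chance has helped. Balance in the sequence cannot be restored once the data are collected.

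**Working it through.** **Inputs.** Ten conditions, and therefore ten periods (II.B); 75 per group, 150 in all (II.C); power computed at 120, or 60 per group (II.E). The documents give no figure for sequence balance or for drift in ratings.

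**The plan's own yardstick.** For the concentration effect, II.E says that "a two-sided paired t-test achieves 80% power to detect an effect size of 0.32 standard deviations of the measurement", "considering 120 participants, a correlation of 0.5" and a two-sided alpha of 0.01. The SD of the paired difference is sqrt(2 x (1 - 0.5)) = 1 SD, so the noncentrality is 0.32 x sqrt(120) = 3.51. The noncentral t distribution gives power of 81.1%, so the stated 80% is reproduced. The detectable 0.32 SD serves below as a scale for the distortions.

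**Predecessor cells.** Each participant contributes 9 transitions over 10 x 9 = 90 ordered pairs, so a group of 75 has an expected 75 x 9 / 90 = 7.5 per cell. Results of 2,000 simulated allocations of independent permutations, set against Williams sequences in blocks of 10:

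| | Independent permutations | Williams blocks |
|---|---|---|
| Smallest and largest cell, 75 per group (mean) | 1.9 and 14.5 | 7 and 8 |
| Chance of an empty cell, 75 per group | about 3% | 0 |
| Smallest and largest cell, 60 per group (median) | 1 and 12 | 6 and 6 |
| Chance of an empty cell, 60 per group | about 16% | 0 |

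A cell of 2 instead of 7.5 has a standard error sqrt(7.5/2) = 1.9 times as large.

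**Session position, 75 per group.**

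| | Independent permutations | Williams, fresh labels per block |
|---|---|---|
| Range of mean position across the ten conditions (95th percentile) | 1.08 (1.55) | 0.16 (0.28) |
| Largest between-group gap in mean position for one condition (95th percentile) | 0.88 (1.32) | 0.14 (0.23) |

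For two given conditions, the chance difference in mean position has SD sqrt(2 x 8.25 x (10/9) / 75) = 0.49 positions, where 8.25 is the variance of a uniform position from 1 to 10.

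**Effect on ratings.** Assume a linear drift of 0.5 to 1.0 SD from first to tenth session, or 0.056 to 0.111 SD per position. Without period adjustment:

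- Typical pair: 0.49 x 0.056 to 0.49 x 0.111, about 0.03 to 0.05 SD.
- Extreme pair (earliest against latest condition): 1.08 x 0.056 to 1.08 x 0.111, about 0.06 to 0.12 SD.

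Both are well below 0.32 SD.

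**Variance cost after adjustment.** Relative to Williams sequences, independent permutations in a group of 75 raise the average variance of a condition contrast by 1.3% with period in the model, and by 2.8% with period and first-order carryover. The average carryover contrast loses 2.9%, and the worst 8.5%.

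**Can both planned interactions be estimated?** Rank of the design matrix for 75 participants over periods 2 to 10, with subject, period and condition effects (rank 92 before interactions):

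| Sequences | + condition x position | + condition x predecessor | + both |
|---|---|---|---|
| Independent permutations | 164 | 172 | 244 |
| One Williams square, fixed labels | 155 | 155 | 155 |
| Williams square, fresh labels per block | 164 | 172 | 244 |

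In a single fixed square each ordered pair occurs at only one position, so the two interactions are completely aliased. Fresh labels in each block remove the aliasing and keep the cells at 7 or 8.

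**The case against.** A reader might infer that the trial uses simple, unrestricted randomisation of order. The documents do not say so: random assignment to a balanced sequence set would fit the same words. What stands is that balance is not required, so the figures for independent permutations describe what the text allows, not what will necessarily be done.

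A reader might also infer that the condition comparisons are biased. They are not. Randomisation makes position imbalance chance noise, and a period term would remove most of its effect at a cost of 1% to 3% in variance. The primary model is less exposed still, because it uses a numeric free-base slope and a two-level concentration, which average over conditions.

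A further objection is that the carryover analysis is exploratory and that balance does not rescue it. That is correct. With 7 or 8 observations, a cell mean has a standard error of about 1/sqrt(7.5) = 0.37 residual SD, so the full 90-cell interaction stays imprecise under any scheme. An additive carryover term is well estimated under either. The washout and mouth rinsing are also real protections.

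Finally, the obvious remedy of one fixed Williams square would harm the plan by making its two interaction checks indistinguishable. That objection is decisive against the fixed square, but not against a square relabelled in every block.

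**Conclusion.** The point holds in a limited form. The plan does not state how orders are generated and asks for no balance, while three of its analyses depend on order and the listed model has no period term. If orders are independent permutations, predecessor cells per group of 75 run from about 2 to 15 and mean position differs by about 1.1 positions between the extreme conditions. Under the proposed scheme these become 7 to 8 and about 0.16. The cell and position figures rest on that assumption about the orders. The distortion in SD units rests also on an assumed drift, for which the documents offer no value. The primary conclusions are not threatened. The case for acting is that the gain in balance, though modest, is nearly free and must be secured before enrolment.

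**What to change.** In Section II.B, replace the sentence on order with a rule along these lines: within each user group, participants are assigned in permuted blocks of 10 to the ten sequences of a 10x10 Williams square; the ten conditions are randomly relabelled onto the square anew for every block; a participant replaced post hoc under the NNAL or plasma nicotine criterion is replaced by one who receives the same sequence. State who holds the list. Adding a period term to the model in Section II.E would complement this and would deal with the residual imbalance.

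The cost is a slightly more complex randomisation list. There are no extra participants, visits or procedures, and blinding is unaffected if the pods remain coded. At 75 per group the last block is half filled, so cells hold 7 or 8 rather than an equal number; exact equality would need a multiple of 10 per group and is not worth changing the sample size for. The plan should also say that the full condition-by-predecessor interaction is descriptive, since its precision stays low under any ordering.

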Each participant will make one laboratory visit, which will take up to 3 hours. After obtaining their informed consent at the study visit, eligibility to participate in vaping sessions will be determined. Smoking status will be biochemically confirmed via an exhaled carbon monoxide reading (eCO) of ≥ 4 ppm and a urine cotinine testing kit, and exclusive EC use status will be confirmed with eCO (< 4 ppm) and the cotinine test, and cross-validated against self-reports.¹⁶ Older adult smokers' 12-hour abstinence from smoking will be confirmed with eCO (≤ 10 ppm). A urine pregnancy test will be

administered if the participant's biological sex is female. Urine sample will be collected and analyzed for the level of total NNAL, a metabolite of NNK that is found only in cured tobacco and is present at extremely low levels in EC users,¹⁶ using validated methods¹⁷⁻²⁰ following study visits. As a semi-bogus pipeline procedure²¹ to improve the truthfulness of self-reports, participants will be told that the urine sample will be analyzed at the time of the visit to confirm current smoking in smokers (≥ 0.15 pmol/mL urine total NNAL) and no concurrent use of combustible and smokeless tobacco use among young adult exclusive EC users (< 0.15 pmol/mL). Those who do not meet the criteria will be replaced post hoc with additional participants. Blood sample will also be collected as a semi-bogus pipeline procedure to confirm nicotine abstinence. Participants will be told that their abstinence will be confirmed at the time of visit via blood plasma nicotine analysis (this is a semi-bogus pipeline as 3mL venous blood sample will not be analyzed in real-time but collected for later analysis and those with baseline plasma nicotine levels ≥ 3 ng/mL will be replaced post hoc with another participant).

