Participants who meet the following eligibility criteria will be included in the study. Inclusion criteria: 1) current exclusive young adult EC user (daily use of ≥ 1 vaping bout, defined as taking around 15 puffs or vaping for around 10 minutes) for at least the past 3 months (confirmed by cotinine test kit) between 21-24 years old with no/minimal history of smoking cigarettes (< 10 cigarettes in entire life), or

current older adult smoker (daily use, ≥ 100 cigarettes in entire life) aged 25-50 years not currently engaged in smoking cessation activities; 2) willing to abstain from all nicotine product and marijuana use for at least 12 hours before the study visit; and 3) read and speak English. Exclusion criteria: 1) currently attempting to quit nicotine or tobacco products; 2) currently pregnant (will be verified with urine pregnancy test), planning to become pregnant, or breastfeeding; 3) use of nicotine products other than ECs or cigarettes (use of ≥ 10 traditional cigars, cigarillos, or filtered cigars in entire life; use of smokeless tobacco products ≥ 10 times in entire life; or hookah in the last 30 days); 4) self-reported diagnosis of lung disease including asthma, cystic fibrosis, or chronic obstructive pulmonary disease; and 5) self-reported new or unstable cardiovascular disease diagnosed within the past 12 months. Upon completion of the study, we will provide participants with information on free tobacco dependence treatment through the Ohio Tobacco Quitline.

3) Participant Identification

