Participants will complete questionnaires on sociodemographics, tobacco use history, and EC and cigarette dependence upon enrollment. Sociodemographic measures will assess participant age, sex (male/female), marital status, ethnicity, employment status, years of education, and annual household income. Tobacco use history will assess years of tobacco use, age of first use, tobacco type, brand, frequency, quantity, and duration of using all nicotine products including cigars, cigarillos, little cigars, pipe tobacco, chewing tobacco, snuff, snus, EC/vape/mod/APV/e-hookah, and hookah tobacco. Cigarette Dependence will be measured with the 10-item Penn State Cigarette Dependence Index²⁸ and the 12-item Cigarette Dependence Scale.²⁹ EC Dependence will be measured with both a modified 12-item EC Dependence Scale and the Penn State EC Dependence Index.^{29,30}

After taking two puffs of each of the 10 study conditions (5 freebase nicotine fractions x 2 nicotine concentrations), participants will complete the General Labeled Magnitude Scale (gLMS)¹⁴ and Labeled Hedonic Scale²³ to rate the liking or disliking of sensation and the strength of sensory attributes

(throat hit, smoothness, harshness, sweetness, bitterness), and a tobacco industry-designed thermometer rating scale of overall acceptance (from 0 “the very worst” to 100 “the very best”, with 50 indicating “indifferent”).²⁴ Participants will also complete the Drug Effects/Liking Questionnaire which will assess the desire and liking of study products, positive and negative effects, and perceived strength and effectiveness.²⁵ The modified Cigarette Evaluation Questionnaire (mCEQ)²⁷ and behavioral intention to continued use²⁶ will also assess subjective responses to ECs (e.g., reward, satisfaction).

2) E-cigarette Device and E-liquids

Study EC Device: JUUL will be used as EC device by all participants during sessions, a refillable pod-based device.

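### The planned covariates include items that barely overlap, or do not overlap, between the two user groups, so adjusted group levels of appeal may rest on extrapolation; secondarily, the subject random effects are not specified.

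*Combined protocol and SAP*

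**What the plan says.** II.E Data Analysis gives the model for the appeal measures: "Models will include demographic and smoking history as covariates, random effects for subject, main effects for user group (smokers vs. EC use". FB fraction, concentration and their interactions with user group follow. The section does not list the covariates, the covariate values at which group levels are read, or the form of the subject random effects.

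The groups are set out in II.A as "young adult (21-24 years) exclusive EC users with no or minimal history of smoking (n=75) and older adult (25-50 years) smokers". II.C.2 adds the smoking criteria. Young users are those "with no/minimal history of smoking cigarettes (< 10 cigarettes in entire life"; the other group is "current older adult smoker (daily use, ≥ 100 cigarettes in entire life) aged 25-50 years". II.B plans a urine check for "no concurrent use of combustible and smokeless tobacco use among young adult exclusive EC users".

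The candidate covariates are in II.D.1: "Sociodemographic measures will assess participant age, sex (male/female), marital status, ethnicity, employment status, years of education" and, for tobacco history, years of use, age of first use, and "brand, frequency, quantity, and duration of using all nicotine products".

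The primary goal in II.E is to "identify a nicotine fraction limit that is appealing to smokers with a minimal appeal to young adult EC users".

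**The concern.** Adjusting for a covariate whose ranges do not meet compares people whom the design cannot enrol. No participant of 25 or over is a young exclusive user, and none of 24 or under is an eligible smoker. Lifetime cigarettes separate the groups in the same way, and any item that measures amount of cigarette smoking largely reproduces user group.

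The goal concerns levels as well as differences: a limit has to appeal to smokers and have minimal appeal to young users. The thermometer scale in II.B has a marked indifference point at 50. Whether a condition lies above or below it in each group cannot be seen from a ranking. If adjusted levels are read at a pooled mean age, the figure for young users describes an age that none of them has.

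The second matter is separate. The interaction tests carry the hypothesis in I.C, and their error rate depends on whether the model lets subjects differ in their response to FB fraction and concentration. The plan leaves that open.

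**Working it through.** **The plan's own figure.** The plan gives no figure for group levels. Its correlation of 0.5 is used below, so I checked how it is meant. For the paired test with n = 120, alpha 0.01 and effect 0.32 SD, the SD of a difference is √(2(1 − 0.5)) = 1 SD and the noncentrality is 0.32 × √120 = 3.51. The noncentral t gives 81.1% power against 80% stated. I therefore take between-subject variance 0.5 and residual variance 0.5, in units of the rating variance.

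**A. Age beside user group**

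Inputs from the documents: 75 per group, 10 ratings each, age ranges 21-24 and 25-50. Assumption: ages uniform in whole years.

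- Young users: mean 22.5, variance (4² − 1)/12 = 1.25.
- Smokers: mean 37.5, variance (26² − 1)/12 = 56.25.
- Squared standardised gap: D² = 15²/[(1.25 + 56.25)/2] = 225/28.75 = 7.83.
- Variance inflation for group: 1 + D²/4 = 2.96, so the standard error is multiplied by √2.96 = 1.72. Age explains 1 − 1/2.96 = 66% of the variation in group membership.
- Unadjusted standard error of the group difference, averaged over conditions: √[(0.5 + 0.5/10) × 2/75] = 0.121 SD. Adjusted: 0.121 × 1.72 = 0.208 SD.
- Smokers' share of the age-slope information: 56.25/57.5 = 98%.

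Other assumed age distributions for smokers:

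| Mean / SD | D² | Standard error multiplied by |
|---|---|---|
| 30 / 5 | 4.29 | 1.44 |
| 35 / 7 | 6.22 | 1.60 |
| 37.5 / 5 | 17.14 | 2.30 |
| 42 / 5 | 28.97 | 2.87 |

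With a smoker SD of 5 their share of the slope information is 25/26.25 = 95%.

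*Reference age.* The pooled mean under uniform ages is (22.5 + 37.5)/2 = 30, six years above the oldest young user.

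*Shift in the estimate.* Suppose the groups as recruited differ by 5 points and appeal falls 0.5 points per year of age in smokers only. The common fitted slope is −0.5 × 0.978 = −0.489, and the adjusted difference is 5 + 0.489 × 15 = 12.3. With no age trend the two differences agree.

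*Amount smoked.* The size depends on how the item is recorded, which the documents do not say. If it were current cigarettes per day, zero in young users and with mean k times its SD in smokers, the inflation would be 1 + k²/2. At k = 1, 2 and 3 the standard error is multiplied by 1.22, 1.73 and 2.35.

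*What does not move.* The interactions are contrasts within subjects. A subject-level covariate entered as a main effect adds the same constant to all ten ratings of a subject and cancels from those contrasts when data are complete and the model is linear. It shifts the group difference equally at every condition, so the ranking of conditions is also unchanged.

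**B. Subject random effects (conditional on an intercept-only fit)**

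Let FB fraction be in SD units, r the residual variance (0.5), and t the between-subject SD of the FB slope, which the documents do not give.

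- True variance of one subject's slope: t² + r/10.
- Variance assumed by an intercept-only fit: r/10 + t²/9.
- q = square root of their ratio. The nominal 1% test rejects 2·P(Z > 2.576/q).

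| t | q | Rejection rate |
|---|---|---|
| 0 | 1.00 | 1.0% |
| 0.1 | 1.08 | 1.7% |
| 0.2 | 1.29 | 4.5% |
| 0.3 | 1.53 | 9.2% |

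For t = 0.2: q² = 0.090/0.0544 = 1.65. At that t the rate is 3.4% if the correlation is 0.3 (r = 0.7) and 7.1% if it is 0.7 (r = 0.3). Simulation with 20,000 replicates and 75 per group gave 1.0, 1.8, 4.6 and 9.0% for the four rows. A t-test on per-subject slopes stayed at 0.9-1.1%.

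**The case against.** The case for leaving the plan alone has real substance.

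- **The covariates are not named.** II.E names neither age nor any particular smoking item. That age is included is an inference, though a natural one: it heads the list of sociodemographic measures and no exception is made. This stands as a limit on the finding.
- **Smoking history does not separate the groups as a whole.** Age of first use and years of tobacco use may overlap. A reader might infer that every history item is collinear with group, or that the model cannot be fitted at all. The documents do not support that. It would need item formats, such as smoking days per month, that II.D.1 does not give.
- **The stated tests are untouched.** II.E judges differential effects by the interactions and looks for the combinations with the largest group difference. Neither the tests nor that ranking changes. A reader might infer that collinearity with age invalidates the test of the hypothesis; it does not. II.E also sets no numerical cut-off for appeal. What remains is that the declared goal is worded in terms of levels.
- **The age ranges abut.** A contrast at about 24-25 years extrapolates very little, and at age 30 only the young users' level is extrapolated. This is correct, but the plan names no reference age.
- **Adjustment answers a legitimate question.** Adjusted and unadjusted contrasts are different targets. The plan does not say which it wants, and an equal-age contrast has little or no support in this design.
- **Random effects may include slopes.** The wording allows them. A reader might infer that the plan specifies an intercept only and so has an inflated error rate. It specifies neither.

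**Conclusion.** The point holds in a limited form. Followed as written, the rule puts demographic and smoking-history covariates beside a group variable that is itself defined by disjoint ranges of age and lifetime cigarettes. If age or an amount-smoked item enters, adjusted group levels and absolute group differences lean on a slope for which smokers supply 95-98% of the information in the age case. The standard error of the group difference then rises about 1.7-fold under uniform ages, and 1.4- to 2.9-fold across the other age distributions tried. These multipliers rest on assumed ages. Any shift in the estimate itself depends on an age trend that the documents do not give, and it is nil if there is none.

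The interaction tests and the ordering of conditions are not in question in a linear model with complete data.

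The random-effects matter is secondary. It is an open specification, and the inflation arises only if an intercept alone is fitted and slopes truly vary between subjects.

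**What to change.** In II.E:

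1. List the covariates. In any model containing user group, omit age and the smoking-amount items that separate the groups, or centre them within group so that each group's level is read at its own mean. Keep covariates that overlap, such as sex and education.
2. State that the group contrast is between the two populations as recruited, not at equal age.
3. State the subject random effects: an intercept plus slopes for FB fraction and concentration. Name a fallback if the fit fails: a two-sample t-test on per-subject slopes.

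**Cost.** Wording only; no new data. Under items 1 and 2 the group difference cannot be attributed to smoking rather than age, but this design cannot separate the two without extrapolation in any case. Under item 3, when slopes vary, interaction intervals are wider than intercept-only ones, by factors of 1.08, 1.29 and 1.53 at slope SDs of 0.1, 0.2 and 0.3, so power is lower than an intercept-only fit would suggest. Convergence problems are possible, hence the fallback.
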